8.5 Subject Replacement Criteria

Withdrawn subjects will not be replaced. If a substantial number of subjects are withdrawn from the study, the sponsor will evaluate the need for developing replacement criteria.

Randomized subjects withdrawn from the study may not reenter. The subject number for a withdrawn subject will not be reassigned to another subject.

9 TREATMENTS

9.1 Identification of Investigational Products or Placebo

The IP used in this study is varespladib-methyl along with matching placebo. Varespladib-methyl will be provided as an oral formulation.

Varespladib-methyl

- Varespladib-methyl (LY333013) is an immediate-release, oval, white, film-coated tablet at a dosage strength of 250 mg for oral administration.
- Scaled pediatric doses of varespladib-methyl (LY333013) are supplied as 50 mg immediate-release capsules for oral administration.

Placebo

- The oral placebo is supplied as a white film-coated oval tablet to match the appearance of the LY333013 250 mg tablet and contains a subset of the excipients present in the active tablet formulation: lactose monohydrate, microcrystalline cellulose, and magnesium stearate.
- Placebo for scaled pediatric dosing is supplied as an immediate-release capsule to match the LY333013 50 mg capsule, and contains the excipients lactose monohydrate, microcrystalline cellulose, and magnesium stearate.

9.2 Selection of Timing of Dose for Each Subject

Varespladib-methyl or placebo will be administered, concurrently with institutional SOC, to subjects with suspected or confirmed snakebite envenoming:

- Adult subjects will receive an initial loading dose of 500 mg (2 x 250 mg oral tablet) varespladib-methyl upon randomization, followed by dosing with 250 mg varespladib-methyl (1 x 250 mg oral tablet) approximately 12 hours later, and subsequent BID dosing with 1 x 250 mg varespladib-methyl oral tablets for the remainder of the 7-day treatment period.
- Pediatric subjects (ages 5 to < 18) will be administered doses of varespladib-methyl determined by allometric scaling, provided as 50 mg capsules.

Tablets and age appropriate capsules may be administered via feeding tube (e.g. naso- or orogastric tubes) in patients requiring mechanical ventilation.

9.3 Dose Adjustment Criteria

Dose adjustment is not planned for this study.

9.4 Treatment Compliance

All hospitalized subjects will receive the IP or placebo at the study site under the surveillance of appropriate study personnel until discharged from the hospital. Tablet and capsule administration details will be recorded by the site. Subjects who are discharged during the 7-day treatment period will be asked to record the date and time of each dose.

9.5 Method of Assigning Subjects to Treatment Groups

In this parallel-group randomized study, subjects who meet study entry criteria will be randomly assigned in a 1:1 ratio to varespladib-methyl or placebo. The randomization schedule will be computer generated using a permuted block algorithm and will randomly allocate IP to randomization numbers. The randomization numbers will be assigned sequentially through a central interactive web response system (IWRS) as subjects are entered into the study. The randomization schedule will be stratified by age group (5 to < 11 years, 11 to < 18 years, and \geq 18 years) and by the presence or absence of neurotoxicity (SSS nervous system subscore of 0–1 or \geq 2) at Baseline, resulting in 6 strata in total. Study center will not be a blocking factor in the randomization schedule. No one involved in the study performance will have access to the randomization schedule before official unblinding of treatment assignment.

The randomization schedule will be prepared by the study contract research organization (CRO) before the start of the study. No subject will be randomized into this study more than once.

9.6 Blinding and Unblinding Treatment Assignment

All subjects, Investigators, and study personnel involved in the conduct of the study, including data management, will be blinded to treatment assignment except for a specified unblinded statistician and programmer from the study CRO who will have access to the randomization code. The unblinded study personnel will not participate in study procedures or data analysis prior to unblinding of the study data to all study-related personnel upon database lock. If an interim analysis is conducted, then unblinded personnel who are not otherwise involved in the study will prepare the data for review.

Study personnel will make every effort to safeguard the integrity of the study blind to minimize bias in the conduct of the study. Treatment unblinding is discouraged if knowledge of the treatment assignment will not materially change the planned management of a medical emergency. Unblinding will be permitted in a medical emergency that requires immediate knowledge of the subject's treatment assignment.

Unblinding should be discussed in advance with the medical monitor, if possible. For emergency unblinding, study personnel will use the IWRS. If the Investigator is not able to discuss treatment unblinding in advance, they must notify the medical monitor as soon as possible about the unblinding incident without revealing the subject's treatment assignment.

Unblinding for an individual subject will not result in unblinding the treatment assignments for the remaining subjects in the study. Thus, the overall study blind will not be compromised. If a subject's treatment assignment is unblinded, he/she may or may not be asked to withdraw from the study. The Investigator will make this decision after consultation with the medical monitor.

9.7 Prohibited and Permitted Therapies

All concomitant medications (including over-the-counter medications and herbal supplements as well as sedatives and paralytics for intubated patients) and concomitant therapies used will be recorded in the source document and on the appropriate eCRF.

9.7.1 Prohibited Therapies

The prohibited therapies prior to enrollment are described in Section 8.2.2.

9.7.2 Permitted Therapies

All medications and therapies for snakebite envenoming, including SOC, are allowed after enrollment in this study. No other experimental therapies are permitted during participation in this study.

Initial inhibition/induction potential of varespladib towards major human CYP450 enzymes have been performed. Data suggest that the active form of varespladib-methyl does not inhibit or induce major CYP450 enzymes. Although varespladib-methyl has been given to over 3,600 subjects with few AEs, limited *in vitro* data exists regarding the potential of varespladib to act as an inducer for P450-mediated metabolism or impact major human transporters. Therefore, the sponsor recommends avoiding use of CYP450 inducers and substrates or inhibitors of major human transporters (but their use is not prohibited) during the period of IP administration based on the Investigator assessment of risk. A list of transporters is included on the FDA.gov Drug Development and Drug Interactions website in Table 5-1 and 5-2 of the Table of Substrates, Inhibitors and Inducers document (FDA, 2020):

- Table 3-3, "Examples of clinical inducers for P450-mediated metabolisms (for concomitant use clinical DDI studies and/or drug labeling) (12/03/2019)"
- Table 5-1, "Examples of clinical substrates for transporters (for use in clinical drug-drug interaction [DDI] studies and/or drug labeling) (12/03/2019)"
- Table 5-2, "Examples of clinical inhibitors for transporters (for use in clinical drug-drug interaction [DDI] studies and drug labeling) (9/26/2016)."

9.8 Treatment After End of Study

After the end of the study, each subject will be treated according to standard clinical practice.

9.9 Dispensing and Storage

The IP and placebo supplied by Ophirex is to be used exclusively in the clinical study according to the instructions in this protocol. The Investigator is responsible for dispensing the IP and placebo according to the dosage scheme and for ensuring proper storage of the products.

Until the IP is dispensed to the subjects, it must be stored in a securely locked area that is not generally accessible. The oral IP and placebo may be stored at room temperature. The key to the storage area is to be kept by the Investigator or designee responsible for the IP. The store will be accessible only to those persons authorized by the Investigator to dispense the products.

Detailed instructions for selecting and dispensing each dose of IP and placebo are in the study manual.

9.10 Drug Accountability

The Investigator or designee must confirm the receipt of the IP with his or her signature. A copy of this receipt must be kept by the Investigator and another copy will be stored at Ophirex, Inc. or designee.

The Investigator or designee must maintain adequate records showing the receipt, dispensing, return, or other disposition of the IP, including the date, quantity, batch or code number, and identification of subjects who received the IPs. The Investigator will not supply the IP to any person except those named as sub-Investigators on the Food and Drug Administration (FDA) form 1572, designated study personnel, and subjects in this study. The Investigator will not dispense the IPs from any study sites other than those listed on the FDA Form 1572. IP may not be relabeled or reassigned for use by other subjects. If any of the IP is not dispensed, or is lost, stolen, spilled, unusable, or received in a damaged container, this information must be documented and reported to the sponsor and appropriate regulatory agencies, as required.

Upon completion of the study, the IP (partly used, unused, and empty packaging, e.g., vials and tablet bottles) must be left in the original packaging and destroyed on site.

9.11 Labeling and Packaging

Labeling and packaging of IP and placebo will be performed by Alcami, Inc., [name].

9.11.1 Labeling

Kits will have labels affixed that meet the applicable regulatory requirements and may include the kit or randomization number, IP, dosage strength, lot number, protocol number, volume or number of tablets/capsules, caution statement, storage, and sponsor identification.

10 STUDY PROCEDURES

Subjects who are able must provide written informed consent and/or assent before any study-related procedures are initiated, including the cessation of prohibited concomitant therapy. As snakebites may constitute life-threatening medical conditions that necessitate urgent intervention, a legally authorized representative may provide consent for subjects who are not able to provide informed consent because of the severity of their condition.

For the timing of assessments and procedures throughout the study, refer to the Schedule of Events (Section 2.2). Throughout the study, every reasonable effort should be made by study personnel to follow the timing of assessments and procedures in the Schedule of Events for each subject. If a subject misses a study visit for any reason, the visit should be rescheduled as soon as possible. In the event that subjects are unable to respond to study visit assessments (i.e., CGI-I, PGIC, PSFS, NPRS, C-SSRS), data from those study visits will be handled as described in Section 10.3.1.

10.1 Study Duration

The overall study duration is expected to be approximately 12 months.

The sequence and duration of the study periods will be as follows:

- 1. Screening/Enrollment/Treatment Duration: 7 days. As subjects are admitted to ED, screening, enrollment, and treatment will take place on the same day.
- 2. Follow-up: approximately 21 days (28 days after initial study intervention).

10.2 Study Periods and Visits

10.2.1 sPLA₂ and Pharmacokinetics Sample Timing

Note that the sPLA₂ and PK sample collection will be performed with a different timing than the other assessments, as described in the Schedule of Events (Table 1).

Specifically, PK sampling will only be performed for a subset of adult and pediatric subjects on Days 1 and 3 and all subjects on Day 7 as described in Section 10.3.2.1. Subjects will be enrolled for PK analysis as follows: Day 1 - 20 subjects, pre-dose and 0.5, 1, 2, 4, 6, 8, and 12 (pre-second dose) hours; Day 3 - 20 subjects, pre-dose and 0.5, 1, 2, 4, 6 hours; Day 7 - all subjects, pre-dose. Special attention should be paid to collection of PK samples on Day 1 of this protocol.

sPLA₂ sampling will be performed for all subjects on Day 1 (pre-dose and 1, 3, 6, and 9 hours post-first dose), and on Day 2, Day 3, and Day 7 (pre-dose).

10.2.2 Screening (Enrollment and Baseline)

Because patients are enrolled after a snakebite with envenoming, each subject must be screened, and treated within the first day (Day 1) of the study. Following completion of all assessments and confirmation of eligibility, the subject will be randomized via the IWRS.

The following critical assessments/procedures must be performed at enrollment, prior to initiation of IP treatment: informed consent, inclusion/exclusion criteria review, medical history, physical examination, vital signs, SSS, Head-Lift, NPRS, and pre-dose laboratory blood draws. The following noncritical assessments should be performed as early as possible, but may be performed after randomization and initiation of study drug and SOC if required due to patient condition: demographic information, height/body weight, 12-lead ECG, grip strength, PGIC, CGI-I, and C-SSRS.

The following procedures will be performed at Screening:

Baseline:

- Obtain informed consent, either from the subject or a legally authorized representative
- Review inclusion/exclusion criteria
- Record prehospital tourniquet use as a snakebite treatment
- Record hospitalization details
- Record pulmonary support interventions
- Perform physical examination
- Measure vital signs per institutional practice
- Perform individual assessments pertaining to the SSS (A scoring sheet for use by study personnel is provided in Appendix A; clinical evaluation of the overall SSS [Appendix B] will be performed after completion of the study):
 - i. Local wound severity
 - ii. Pulmonary severity
 - iii. Cardiovascular severity
 - iv. Gastrointestinal severity
 - v. Hematologic severity (do not wait for laboratory results)
 - vi. Renal severity (do not wait for laboratory results)
 - vii. Nervous system severity
- Measure Head-Lift duration (0 to 5 seconds)
- Perform NPRS
- Collect blood and urine for the following laboratory assessments:
 - i. CBC

Ophirex, Inc.

Confidential

OPX-PR-01

- ii. Serum chemistry
- iii. CK
- iv. LFTs
- v. eGFR
- vi. Hemolysis (Free hemoglobin, haptoglobin, lactate dehydrogenase [LDH])
- vii. Prothrombin time (PT), partial thromboplastin time (PTT), thrombin time, INR
- viii. Absolute fibrinogen
 - ix. Urinalysis
 - x. sPLA₂ (see Section 10.2.1)
- xi. Urine pregnancy
- xii. Serum pregnancy test (subjects of childbearing potential only)
- xiii. Biomarkers (C-reactive protein [CRP], and D-dimer)
- Collect samples for PK analysis from subset of subjects (see Section 10.3.2.1)
- Confirm and record details of snakebite envenoming. Obtain photographic documentation where feasible
- Assess and record demographic information (may be performed after randomization treatment should not be delayed)
- Assess and record medical history, including time of bite, current medications (e.g., prescription and nonprescription medications) and therapies including antivenom use and analgesics (may be performed after randomization, treatment should not be delayed)
- Measure weight and height (may be performed after randomization treatment should not be delayed)
- 12-lead ECG (may be performed after randomization treatment should not be delayed)
- Measure grip strength (may be performed after randomization, treatment should not be delayed)
- Perform PGIC (may be performed after randomization, treatment should not be delayed)
- Perform C-SSRS (Baseline/Screening Form; if subject is unable to respond, perform C-SSRS as early as clinically possible on Day 1, screening and randomization should not be delayed for C-SSRS performance)
- In sedated, endotracheally intubated subjects, perform additional assessments according to instructions in Section 10.3.1.7.
- Perform baseline CGI-I. Baseline CGI-I should be assessed compared to patient's previous clinical status.
- Randomize subjects and assign IP to treatment and placebo arms

OPX-PR-01

Procedures for rescreening prospective subjects who initially fail to meet study entry criteria are described in Section 14.3.

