8.2 Study Entry Criteria

8.2.1 Inclusion Criteria

A subject will be eligible for study participation if he or she meets all the following criteria:

- 1. Is a male or female \geq 5 years of age with venomous snakebite.
- 2. Index event (snakebite) must be symptomatic and symptom onset must have occurred within 10 hours of eligibility assessment.
- 3. Patients must meet one of two categories of inclusion criteria:

Category 1: The patient has not yet completed first dose of antivenom:

SSS inclusion score* of ≥ 2 in one system and ≥ 1 in another system (2+1) **OR** ≥ 3 in at least one system.

OR

Category 2: The patient has completed an initial dose of antivenom:

SSS inclusion score* of ≥ 2 in one system and ≥ 1 in another system (2+1) OR ≥ 3 in at least one system **AND** CGI-I score of ≥ 5 (i.e., minimally worse, much worse, or very much worse).

- 4. Is willing (or legally authorized representative is willing) to provide informed consent prior to initiation of any study procedures.
- * Only local wound, pulmonary, cardiovascular, hematologic, or nervous system scores qualify for SSS inclusion criteria. GI and Renal scores are not used for inclusion. Hematologic score may be counted if available, but inclusion should not wait for laboratory results. Point of care tests (e.g., 20WBCT) may be used for enrollment, if used per site standard of care (see Appendix A).

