8.2.2 Exclusion Criteria

A subject will be excluded from the study if he or she meets any of the following criteria:

OPX-PR-01

1. Is considered by the Investigator to have a clinically significant upper GI bleed evidenced by significant hematemesis, "coffee-ground" emesis or nasogastric aspirate, hematochezia thought to originate from upper GI tract.

- 2. Has history of CVA or intracranial bleeding of any kind, acute coronary syndrome, MI, or severe pulmonary hypertension.
- 3. Has known history of inherited bleeding or coagulation disorder.
- 4. Is, at Screening Visit, using the following anticoagulants: warfarin/coumadin, argatroban, bilvalirudin, lepirudin, apixaban, dabigatran, clopidogrel, prasugrel, ticlodipine or another anticoagulant agent not specifically listed, or has used heparin, enoxaparin, fondaparinux, or other low molecular weight heparin or antiarrhythmic drugs within 14 days prior to treatment.
- 5. Has a history of chronic liver disease such as chronic active viral hepatitis, alcohol-related liver disease, non-alcoholic steatohepatitis, non-alcoholic fatty liver disease, hemochromatosis, primary biliary cirrhosis, primary sclerosing cholangitis, autoimmune hepatitis.
- 6. Reports or has known pre-existing renal impairment or chronic kidney disease.
- 7. Has a known allergy or significant adverse reaction to varespladib-methyl.
- 8. Is considered by the Investigator to be unable to comply with protocol requirements due to geographic considerations, psychiatric disorders, or other compliance concerns.
- 9. Is pregnant, has a positive serum human chorionic gonadotropin (hCG) pregnancy test or not willing to use a highly effective method of contraception for 14 days after initial treatment, or is breast-feeding.

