11.3 Special Considerations

11.3.1 Adverse Events of Special Interest

Investigators should specifically monitor several AEs associated with varespladib treatment, including cerebrovascular accident (CVA; stroke), MI, and malignant cardiac arrhythmias. However, these AEs may also be associated with many snakebites.

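### Protocol 10.2.2 contradicts the entry criteria, and itself, on whether CGI-I and medical history must be known before randomization and first dose

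*Protocol*

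**What the plan says.** Inclusion criterion 3 (Protocol 8.2.1) splits patients by whether they have completed an initial antivenom dose. Those who have (Category 2) must reach the SSS threshold and also have a "CGI-I score of ≥ 5 (i.e., minimally worse, much worse, or very much worse". Appendix A, the inclusion scoring sheet, repeats this.

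The introduction to Protocol 10.2.2 places randomization after the assessments are finished and eligibility is confirmed. It then gives two lists. The critical list must precede study drug and contains "inclusion/exclusion criteria review, medical history, physical examination, vital signs, SSS, Head-Lift, NPRS, and pre-dose laboratory blood draws". Items on the noncritical list may be left until after allocation, even past "initiation of study drug and SOC if required due to patient condition: demographic information, height/body weight, 12-lead ECG, grip strength, PGIC, CGI-I, and C-SSRS".

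The procedure list later in the same section treats medical history differently. The history item covers when the bite happened, what the patient is taking and whether antivenom was given. It ends: "therapies including antivenom use and analgesics (may be performed after randomization, treatment should not be delayed". The item for the baseline CGI-I has no deferral note and stands directly before the randomization item.

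In Table 1 the pre-dosing cell for CGI-I is empty and the first mark stands in the 0 h dosing column, with a footnote that treats it as the baseline rating. Medical history is marked pre-dosing, without the footnote that permits deferral.

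**The concern.** An entry criterion works only if it is checked before allocation. If CGI-I is rated after the first dose, a patient who has had antivenom and is not worsening may already be randomized and treated. The ITT population is everyone randomized (Protocol 13.1.1, SAP 5), so that patient stays in the primary analysis, outside the group that Category 2 describes.

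The history conflict has a safety side. Exclusion 2 reads "Has history of CVA or intracranial bleeding of any kind, acute coronary syndrome, MI, or severe pulmonary hypertension". Protocol 11.3.1 asks investigators to watch for "several AEs associated with varespladib treatment, including cerebrovascular accident (CVA; stroke), MI, and malignant cardiac arrhythmias", and Protocol 5.3 answers the stroke and infarction cases seen in earlier trials by saying that such patients are excluded here. That safeguard depends on the history being known before the dose.

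There is also a measurement side. Later CGI-I ratings are made against the baseline rating (Protocol 10.3.1.2), and SAP 8.1.2.4 names baseline CGI-I as a covariate for the key secondary endpoint at Day 2. A rating made after dosing is not a clean baseline.

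**Working it through.** No figure in the plan is in dispute, so the check is a comparison of texts.

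| Input | What it decides | Text placing it before | Text letting it come later |
|---|---|---|---|
| CGI-I, Category 2 | Inclusion 3 (8.2.1, Appendix A) | 10.2.2: eligibility confirmed before randomization, criteria review before study drug; procedure item has no deferral note | 10.2.2 noncritical list: after randomization and study drug, if the patient's condition requires; Table 1: first mark at 0 h |
| Medical history, current medication | Exclusions 2 to 6 (8.2.2) | 10.2.2 critical list: before study drug; Table 1: pre-dosing, no deferral footnote | 10.2.2 procedure item: may follow randomization |
| Antivenom status | Category 1 or 2 (8.2.1) | As for history | Same procedure item |
| Age | Inclusion 1, stratum, dosing band | 9.5: age group needed to randomize; 7.3: it determines tablet or capsule | 10.2.2: demographics deferrable |

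**CGI-I.** The general rule and the item-level rule cannot both be followed for a Category 2 patient whose rating is deferred. Eligibility cannot be confirmed while one of its components is outstanding. The deferral applies only when the patient's condition requires it. The notes to Figure 1 describe snakebite patients as critically ill, so that condition may well arise, but the documents do not say how often.

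**History.** Exclusions 2 to 6 cover vascular history, inherited bleeding disorders, anticoagulant or antiarrhythmic use, chronic liver disease and kidney disease. That is 5 of the 9 criteria. The procedure item defers history past randomization, not expressly past dosing. Protocol 7.1 asks for no delay between randomization and study drug, so the two texts together can put history after the dose, against the critical list. This deferral is not limited to patients whose condition requires it.

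**Age.** There is no real gap here. A patient cannot be stratified or dispensed study drug unless the age group is known, so only the recording of demographics is deferred.

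**Size, CGI-I part.** The number of patients wrongly entered would be

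randomized × Category 2 share × share of those with CGI-I deferred past dosing × share of those then rated below 5.

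Only the first term is given (about 110). An assumed Category 2 share of 10% to 50% gives 0.10 × 110 = 11 to 0.50 × 110 = 55 patients in the category. That counts everyone the criterion applies to, not those misenrolled, and it still rests on an assumed share. The history part has no usable term beyond the number randomized.

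**The case against.** The strongest reply is that the protocol already has the gate. Section 10.2.2 requires the criteria review before study drug and confirmed eligibility before randomization. Section 8.1 bars anyone who fails a criterion, and Appendix A puts CGI-I on the inclusion sheet. The CGI-I procedure item carries no deferral note, and the column position in Table 1 is weak evidence, since its footnote calls the mark a baseline rating. Fast treatment is deliberate, and deferring CGI-I does no harm in Category 1, where it is not a criterion.

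Most of this stands. It rules out the reading that the protocol simply permits dosing before eligibility is checked: a site that did so would breach several other sentences. It also rules out the claim that history may plainly be taken after dosing, because the deferral names randomization only and the critical list says otherwise. What remains is that the more specific instruction points the other way for an item that is itself an entry criterion.

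A second reply is that misenrolment is handled later. Protocol 8.4 covers patients found to meet an exclusion after entry, the per-protocol analysis removes significant deviations, and SAP 6.1.2 and 8.1.1 use prior antivenom as a sensitivity covariate and a subgroup. These help with interpretation, but they act after exposure and leave the ITT result unchanged. Section 8.4 also cites exclusion criteria 6, 7 and 10 for liver, renal and pregnancy findings, while 8.2.2 has nine criteria and numbers those topics 5, 6 and 9. Those passages must be reconciled too.

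**Conclusion.** The point holds as an internal contradiction. Protocol 10.2.2 conflicts with 8.2.1 and Appendix A on CGI-I for patients who have completed an initial antivenom dose, and its two lists conflict with each other on medical history. It is worth correcting because the texts govern who may be dosed, and a criterion rated after the dose screens no one out while ITT keeps the patient.

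The size is unknown. The documents give neither the Category 2 share nor how often ratings or history are deferred, so neither a count nor a loss of power can be stated. A reader might infer a bias between the arms. The documents do not support that: allocation is randomized and blinded, and deferral applies to both arms alike. The effect at issue is on who is entered and exposed. A reader might also add demographics to the list, but age group has to be known to stratify and dispense. The CGI-I conclusion rests on the wording of 10.2.2 and does not need the layout of Table 1.

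**What to change.** Reconcile Table 1, 8.2.1, 8.2.2 and both lists in 10.2.2 so that three things are obtained before randomization:

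- whether an initial antivenom dose has been completed;
- if so, the CGI-I rating, with the Table 1 mark for these patients moved to pre-dosing;
- the history and medication facts needed for exclusions 2 to 6.

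Leave CGI-I in Category 1, the rest of the history and the recording of demographics deferrable. Have the IWRS ask for antivenom status and, if the answer is yes, the CGI-I value before it allocates.

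The cost is protocol wording and one or two IWRS fields. CGI-I is a single clinician rating, and the history facts are already on the critical list, so the burden on sites is a brief extra step before allocation. For patients already enrolled, a blinded listing before database lock of the baseline CGI-I value and its time relative to first dose, where the eCRF holds that time, would replace the unknown size with a count.
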